### Qualitative semi-structured interviews with men

The interviews will be conducted by a trained male interviewer. Interviews will employ a topic guide that will explore men's sexual relationships with young women, their risk reduction strategies, including familiarity with PrEP, their attitudes towards PrEP as a prevention strategy, how they would feel if they used PrEP, and how they would feel if their partners were to use PrEP with/without telling them. The interview will last approximately 45 minutes to one hour, depending on extent of partnerships and sexual behavior.

**Pilot Study:** Gender-enhanced (GE) virtual interactive-group workshop vs Individually-accessed condition for women.

Self-assessment procedures. Participants will complete self-administered assessments sent through a link to their phones prior to participating in the GE or IA online condition, prior to the workshop, immediately afterwards, and at 3-month follow-up. These self-administered questionnaires will be programmed using Qualtrics, an online survey platform that is housed in the New York State Psychiatric Institute.

HIV testing procedures. HIV infection status (for those who choose to undergo it) will be assessed using a the standard protocol being employed at the MRC GHRU (as described above) This is not a required part of study participation and will not involve retaining biological samples used for HIV testing.

Clinical records. The study nurse will retain her own private clinical records, following the standard HIV counseling and testing protocol. Only data relevant to the study outcomes will be included in study records

Study outcomes – Primary outcome. Undergoing an individual discussion with the study nurse about the possibility of taking up PrEP is the primary behavioral target of the study; undergoing HIV self-testing guided by the study nurse (either in-person at the GHRU office or via telehealth visit) is a secondary outcome, as is uptake of PrEP, if eligible. These outcomes will be documented by the study nurse and at the 3-month **structured survey interview**. The 3-month **survey interview** also will assess other HIV- and pregnancy-prevention methods used. Other outcomes of interest include "stage of change" regarding PrEP uptake, use of contraception, HIV testing with a partner, changes in mediators, talking with partner and/or friends about HIV prevention or PrEP.

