We also will ascertain women's use of PrEP and other prevention strategies through the follow-up interview (self-report).

Acceptability of the workshops will be assessed with items such as *the workshop was fun, boring, too long, too short; I didn't understand most of what was going on; I would recommend the workshop to a friend*. Feasibility of the workshops will be assessed using tracking data for (number attended, number who agreed to be PHAs) and facilitators' summary reports documenting any challenges.

**Acceptability and feasibility of Peer Driven Recruitment.** Data for indicators of acceptance and successful contacts will be obtained by tracking the number of women who agree to be PHAs and take referral coupons and, for each PHA, the number of recruits who meet eligibility criteria and attend the workshop. **Reach** will be assessed by proportion of recruits who (1) score *high* on the risk tool and (2) have never been tested and never attended a family planning clinic (an indicator of reach into networks unconnected to care). The pre- and post-workshop assessments are expected to take 15-20 minutes; the follow-up assessment is expected to take 20 to 40 minutes, depending on use of PrEP.

**In-depth Brief telephone** interviews will cover topics related to outcomes of the interventions, any behavior changes including PrEP uptake that were adopted, and their experiences in successfully recruiting (or not) other women to the intervention.

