by the Gender and Health Research Unit of the Medical Research Council to counsel women around PrEP and conduct HIV counseling and testing, either in person at the MRC office or via a telehealth nurse visit. HIV testing will be done using Oraquick®, an MRC-approved HIV self-test kit, either at the MRC office or offsite by the woman herself, with guidance from the nurse. We therefore propose to revise the primary study outcome to the following: ***having an individual discussion with the study nurse about taking up PrEP (either in-person or via telehealth). Undergoing HIV self-testing guided by the study nurse (either in-person at the GHRU office or via telehealth visit) will be a secondary outcome, as will initiating PrEP if eligible for PrEP (HIV-negative).***

These outcomes will be measured as follows: On the post-test assessment, women will be asked if they wish to speak with the study nurse about PrEP (and/or about any other issues). A “yes” response will trigger a notification to project staff, who will inform the study nurse. The study nurse will then contact the individual participant to arrange the counseling session. The study outcome will be considered to have been enacted when the participant has a PrEP counseling session. This, along with the result of PrEP counseling (e.g., underwent HIV testing or not, PrEP-eligible or not, and will initiate PrEP or not), will be documented by the nurse.

The revised specific aims of this study are as follows:

1. **Formative Work (no changes):** To ***inform intervention development*** through
  - a. Focus groups (six) with at-risk AGYW aged 18-25, grouped by age and recruitment venue (community, family planning clinic) to explore knowledge of, beliefs about, motivators for, and concerns about PrEP in the context of gendered relationship dynamics and PrEP-related stigma;
  - b. Qualitative interviews with men (10 known HIV-positive and 10 HIV-negative or of unknown status) who have female partners aged 18-25 to understand men’s views of PrEP and of their partners’ use of PrEP.
2. **Intervention development (revised):** In collaboration with an Intervention Development Working Group (IDWG) of AGYW, to ***develop a virtual group-based Gender-Enhanced PrEP Information-Motivational workshop***, drawing on our formative Aim 1 data and strategies from our prior HIV prevention interventions, ***and to choose a PrEP video and a PrEP informational website for the individual digital access control condition.***

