## Data Analysis

Workshops: Compare women randomized to the virtual group-interactive workshop with those randomized to individually-accessed links to a PrEP promotional video and PrEP information on the **primary outcome of having an individual discussion with the study nurse about the possibility of taking up PrEP; undergoing HIV self-testing guided by the study nurse (either in-person at the GHRU office or via telehealth visit) (secondary outcome); if eligible for PrEP, initiating PrEP (secondary outcome)**, and, for all women, changes in hypothesized mediators (information, risk perception, gender barriers, outcome beliefs, PrEP-stigma, peer norms) post-intervention and at 3-month follow-up.)

To compare the **primary and secondary outcomes** across the two workshop conditions, we will use generalized linear models (GLM) with a logit link function and the method of generalized estimating equations (GEE) to account for the effect of clustering within recruitment chain. The logit link function is appropriate because the primary and secondary outcomes are dichotomous and characterized as yes/no if achieved at any time over the course of the study by the time of the 3-month follow-up interview. Intervention condition (Gender-Enhanced or Individual Access) is the primary predictor. Although the original data analysis plan also specified accounting for clustering by workshop group attended, we will not account for clustering by workshop group because women in the IA condition received the intervention as individuals rather than as groups.

We will adjust for any substantial baseline differences by condition on age. We will also adjust for any substantial differences by other demographic and behavioral characteristics, such as education level, whether attending school, has a primary partner, sexual risk behaviors (to be defined), relationship power, reported intimate partner violence if these factors differ substantially by condition at baseline and are also associated with the outcome (i.e., meet the conditions of confounding).

To assess if being a PHA, i.e., talking to other women about HIV prevention serves as an additional intervention dose, a secondary analysis will include a variable for whether the woman served as a PHA and recruited other workshop attendees (yes/no).

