**Mediators.** “Other outcomes” include those measures designed to tap constructs that are hypothesized in our theoretical model to be mediators, i.e., on the pathway between the intervention and the outcome. These are factors that we believe influence the outcome (women considering PrEP for themselves) and that if changed by the intervention will lead to an increase in this outcome. We want to know if these factors are influenced by the gender-enhanced intervention and help explain (mediate) any changes in the main outcomes. These hypothesized mediators, most of which are summary measures from multi-item scales, include PrEP information, perceived risk for HIV, perceived effectiveness of PrEP, positive outcomes of taking PrEP, gendered HIV prevention barriers related to partner disclosure, PrEP-related stigma, normative beliefs, medication beliefs. Please see the related document entitled “Table of pilot study measures 2022 June 22.” for descriptions.

An additional variable—stage of change for adopting PrEP--was added when we revised the study. This will also be considered a mediator, although at 3month followup, the last option of this measure is “I am taking PrEP”. This is the indicator for the outcome of initiating PrEP.

For the mediators, we will first test if the intervention had any effect on them, using generalized linear models (GLM) with an identity link function and GEE (to account for clustering effects) to compare the mean difference between the two intervention groups from post-test to pre-test, and from 3-month follow-up to post-test, to determine if there is an increase, decrease, or no change over time (difference of difference analysis), adjusting for age and other confounders if necessary. As per [name]: the model is of the form:

$E(Y|X,T1,T2)=\text{constant}+b1*X+b2*T1+b3*T2+b4*X*T1+b5*X*T2$ , where X is the intervention indicator, T1 and T2 are post-intervention and 3-month FU indicator respectively. The regression coefficient b4 represents the group difference in change of the outcome Y (i.e., the potential mediators) from pre- to

post-intervention, however, it is b5-b4 (NOT b5) that represents the group difference in change of Y from post-intervention to 3-month FU.

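### The SAP scores PrEP initiation by current use at 3 months, against its own any-time rule, and the supplied documents give no rule for combining the sources

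*SAP*

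**What the plan says.** **SAP, Data Analysis.** Initiating PrEP is listed as "if eligible for PrEP, initiating PrEP (secondary outcome". All primary and secondary outcomes are dichotomous and are "characterized as yes/no if achieved at any time over the course of the study by the time of the 3-month follow-up interview".

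**SAP, Data Analysis, Mediators.** A stage-of-change measure was added when the study was revised. At 3 months its last option is a present-tense statement that the woman is taking PrEP. Of that option the SAP says: "This is the indicator for the outcome of initiating PrEP".

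**SAP, December 2020 Revisions.** The nurse documents the result of counselling: "underwent HIV testing or not, PrEP-eligible or not, and will initiate PrEP or not". The last item is an intention, not an observed start.

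**Protocol, Assessment Instruments, Study outcomes.** Nurse-guided HIV self-testing "is a secondary outcome, as is uptake of PrEP, if eligible. These outcomes will be documented by the study nurse and at the 3-month" survey. The same section says staff will ascertain women's "use of PrEP and other prevention strategies through the follow-up interview (self-report"), and that "the follow-up assessment is expected to take 20 to 40 minutes, depending on use of PrEP".

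**SAP, Power Considerations** (carried over from the original proposal). Uptake of PrEP, yes or no, is among the parameters called mission-critical for planning the later randomized trial.

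**The concern.** Ever having started PrEP and taking it on the day of a survey are different quantities. The any-time rule describes the first and the named indicator measures the second. Two analysts, each following one of the two statements, could report different results for the same secondary outcome.

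The loss need not be symmetric. The indicator removes women who started and then stopped. If more of them stop in one arm, the reported difference mixes an effect on starting with an effect on staying on PrEP. The original proposal, reproduced at the head of the SAP, listed uptake and 3-month retention as separate secondary outcomes. The revised aims keep only initiation, yet the indicator now attached to it resembles retention. The revision itself is not an error; the earlier list only shows that the team saw these as two quantities.

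**Working it through.** The plan states no figure for initiation, so there is none to reproduce. The check has two steps: set the definitions side by side, then see what the difference does to an arm comparison.

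**Step 1. How each source would score the same woman**

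| Woman | Any-time rule | 3-month indicator | Nurse entry as the SAP words it |
|---|---|---|---|
| Starts, still taking at 3 months | yes | yes | depends on what she said at counselling |
| Starts, stops before the survey | yes | **no** | depends on what she said at counselling |
| Tells the nurse she will start, never does | no | no | **yes** (intention) |
| Starts, does not complete the survey | yes | **missing** | depends on what she said at counselling |
| Never starts, never intends to | no | no | no |

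The any-time rule and the indicator agree for everyone only if no starter stops before the survey and every starter completes it. Adding the nurse entry by a simple either-or would not repair this, because as worded it records an intention. The Protocol (PrEP clinical assessment) says that the study does not supply PrEP and refers women to a hospital programme. No study dispensing record is described that could settle a disagreement.

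**Step 2. Effect on the comparison**

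Let p be the proportion who ever start and s the share of starters who have stopped by the survey, with complete surveys. The indicator then reads p(1 − s) in each arm. The difference between Gender-Enhanced (GE) and Individual Access (IA) is

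p_GE(1 − s_GE) − p_IA(1 − s_IA).

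- Equal stopping: the difference becomes (1 − s)(p_GE − p_IA), so it shrinks towards zero.
- Equal initiation p: the difference becomes p(s_IA − s_GE), so unequal stopping alone creates a difference.

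The rates below are **assumptions for illustration**; the documents give none.

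| True start, GE vs IA | Stopping, GE / IA | Indicator reads | Difference (true) |
|---|---|---|---|
| 45% vs 30% | 20% / 20% | 36% vs 24% | +12 (+15) |
| 45% vs 30% | 40% / 40% | 27% vs 18% | +9 (+15) |
| 45% vs 30% | 60% / 60% | 18% vs 12% | +6 (+15) |
| 45% vs 30% | 40% / 20% | 27% vs 24% | +3 (+15) |
| 45% vs 30% | 20% / 40% | 36% vs 18% | +18 (+15) |
| 30% vs 30% | 40% / 20% | 18% vs 24% | −6 (0) |
| 30% vs 30% | 20% / 40% | 24% vs 18% | +6 (0) |

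For example, 0.45 × 0.6 = 0.27 and 0.30 × 0.8 = 0.24, which gives +0.03.

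One scale does not depend on assumed rates. The Protocol expects about 50 women in the GE arm. With 50 as the denominator, each woman who started and stopped moves her arm by 1/50 = 2 points, and by more if only eligible women are counted.

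**The case against.** The case on the other side is substantial, and parts of it stand.

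- **The sentence is an aside.** It sits in the Mediators text and explains an overlap between a mediator and an outcome. The any-time rule sits with the outcome models and could be read as governing. That reading is available, but the SAP calls the response the indicator for the outcome and points to no other item. The conflict remains until the SAP says which statement rules.
- **The measures table is unseen.** The SAP refers to a separate table of pilot measures, which was not supplied. It may hold an ever-use item or a scoring rule, and the survey-length remark in the Protocol suggests that further PrEP questions exist. This stands: no combining rule appears in the documents supplied, and no more can be said.
- **Understatement is conditional.** This stands. If nobody stops before 3 months and all starters answer the survey, the two definitions coincide.

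A reader might also infer stronger points that the documents do not support.

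- **That the later trial would be underpowered.** This depends on invented rates. Take 50 per arm, an exact one-sided 90% upper limit for the reference rate, a 15-point difference, an 80% target and no clustering. With a true reference rate of 30%, power is 82% with no stopping and 81%, 79% and 74% at 20%, 40% and 60% stopping. With a true rate of 10%, it stays at 87%, 85% and 81% at the same stopping rates. The argument also needs the later trial to use a different definition from the pilot, and the SAP's own planning example concerns PrEP risk screening, not uptake.
- **That initiation should be compared in all women randomized.** The SAP does open with "Compare women randomized to the virtual group-interactive workshop with those randomized", but it words this outcome as conditional on eligibility and contrasts it with mediators measured in all women. Changing the denominator would change the outcome and is a separate matter.
- **That any use after enrolment is a first start.** The entry criteria exclude women currently taking PrEP or planning to begin, not past users, so a restart is possible.

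**Conclusion.** The conflict is real and should be fixed. As written, the SAP gives initiation two definitions that disagree for any woman who starts and stops before 3 months. The named indicator can understate initiation, and it can shift the arm difference in either direction if stopping differs by arm. Its size cannot be known from the documents; the percentages above show direction and mechanism only.

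The reach is limited to one secondary outcome in a pilot that does not claim power for hypothesis tests. The primary outcome, a nurse discussion documented by the nurse, is untouched. What raises it above a wording quibble is that PrEP uptake is listed as a mission-critical planning parameter, and a planning parameter needs a single definition. The conclusion rests on reading the response option as current use, which its present tense supports, and on the unseen measures table not already resolving the point.

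**What to change.** Replace the sentence in the Mediators text with a definition that follows the any-time rule, for example:

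> Initiation is any PrEP use between enrolment and the 3-month survey, as reported at the 3-month survey or documented by the nurse as an actual start. A recorded intention to initiate does not count.

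Then:

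1. Report taking PrEP at 3 months separately, labelled as current use.
2. Use only sources collected in the same way for all women in both arms. Do not use the roughly 40 brief telephone interviews to score the outcome. They cover PrEP uptake, but only in a selected subset of willing women, who would get an extra chance to be scored yes.
3. Rely on nurse documentation of an actual start only if such a record exists in the same form for both arms; the SAP describes only an intention entry.
4. State how disagreements between sources are resolved and how women without a 3-month survey are scored.
5. If no ever-use item was asked, keep the existing response but call the result current PrEP use at 3 months, not initiation.

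The cost is SAP wording. The subgroup counts in the SAP's effect-modifier section, updated in December 2022, suggest that data were already in hand, so questions probably cannot be added. If ever-use was not asked of everyone, initiation may be recoverable only in part, and the report should say so.

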Sexual risk. High-risk will be defined as having unprotected vaginal or anal intercourse with a partner of unknown or HIV-positive status. Other risk factors considered will include number of partners (and number of HIV+ or unknown status) with whom one has unprotected sex, having a partner 10 or more years older or aged 35-44, experiencing IPV, social network members engage in transactional sex and/or experience IPV.

Hypothesized mediators and effect modifiers to be ascertained at each assessment include **PrEP information**-what PrEP is, common side effects, consequences of PrEP nonadherence (sample items: *most PrEP-related side effects are short-term; PrEP is highly effective in preventing HIV when taken every day*). **Perceived risk** will be assessed with the Perceived Risk of HIV scale ( $\alpha = .91$ ) (54) (sample item, *What is your gut feeling about how likely you are to get infected with HIV?*) (3), and modified to assess perceived risk for pregnancy. **Peer norms around PrEP** will be adapted from the 6-item social norm scale developed by Fernandez and colleagues ( $\alpha = .82$ ) (55) (sample items, *My partner/family would support my using PrEP*); **Positive and negative outcome expectancies of using PrEP** will be developed based on FG findings (e.g. *If I use PrEP, I will avoid conflict with my partner; my partner will object; my partner will abuse me; I will be less worried about getting HIV*), including items tapping **PrEP-related stigma** (e.g. *if I use PrEP, people will think I am promiscuous; people will think I am HIV-positive*); **PrEP attitudes**, developed from FG findings (*PrEP is a good option for me; I feel PrEP is safe to take; I feel PrEP will protect me from HIV*). **Gendered HIV prevention barriers** based on our work in a prior intervention trial (e.g., *it is the man's prerogative to use HIV protection or not; if I use HIV prevention it means I don't trust my partner; my partner could punish me*), and **self-efficacy for PrEP** (e.g., *I would be able to take the PrEP tablets every day even if I sometimes didn't feel well; if I worried that someone would see the tablets, I was short on time, I went to my boyfriend's house*). We also will assess relationship factors, including baseline experience of IPV (56), acceptability of IPV and endorsement of traditional gender norms in relationships (57). These factors may alter (modify) the effectiveness of the GE intervention.

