Power Considerations. The primary goal for this pilot work is to collect preliminary data regarding feasibility, acceptability and target outcomes for the proposed intervention. In line with guidelines from PA-17-166: *Formative and Pilot Intervention Research for Prevention and Treatment*, which caution against using pilot studies (where the sample size is of necessity small) to obtain an estimate of an effect size, we will use these pilot data to rule out unusually large or small true effects through standard 95% confidence interval procedures. We will confirm extrinsic effect sizes are contained within our confidence intervals from the pilot. We will examine the distribution of each variable, and calculate summary statistics by intervention condition. We will estimate key intervention parameters with sample means and proportions together with two-sided 95% confidence intervals, and test the primary null hypotheses at the traditional two-sided level  $\alpha=.05$  (simulation of the subsequent RCT). For planning the RCT, we will also consider one-sided 90% confidence limits for mission-critical *design parameters* such as standard deviations and reference group endpoint rates and proportions in the conservative direction. This is because we intend to plan sample size for the RCT so that power will be “excellent” (at least 80% power) for the clinically relevant effect size to be specified. This strategy will make proper allowance for the limited sample size of the pilot study with its consequent uncertainties, and still yield appropriate sample sizes for the RCT. “Mission-critical” parameters include proportions for dichotomous endpoints (uptake of PrEP clinical assessment, uptake of PrEP yes/no); means and standard deviations for continuous potential mediators of outcome (e.g. gender barriers, PrEP-stigma). Large sample sizes are not required to locate these parameters approximately, but adequately, for planning the subsequent trial, whereas testing the study hypothesis in the pilot

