will generally not have sufficient statistical power. Estimation of mission-critical design parameters with point and confidence interval estimates will be considered highly important; continuous outcome measures make it feasible to detect promising effect effects even in small samples. For the continuous measures, means and standard deviations (sd) will be estimated. For approximately normally distributed variables, an upper one-sided 90% confidence limit for the sd,  $\sigma_u$ , will be constructed from  $\sigma_u = s \chi^2_{v,10}^{1/2}$ , where s is the sample sd and  $\chi^2_{v,10}$  is the upper 10th percentile of the chi-squared distribution with v degrees of freedom. For approximately log-normally distributed variables, a logarithmic transformation will be applied to achieve approximate symmetry and normality. For the dichotomous variables (such as the primary and secondary outcomes, or the PDR performance criteria), exact binomial methods will be employed for the CIs for proportions. As an example, the width of the exact 95% confidence interval around a point estimate of 40% (e.g., percent women who score high-risk) would be 30%-50% with 100 participants.

While testing the primary null hypothesis is not the primary goal for this pilot study, if we assume the proportion of women who undergo PrEP clinical assessment in the information-only group ranges from 20% to 50%, with total sample size of 100 participants we are still able to declare a difference of 33 to 36 percentage points as statistically significant at 0.05 level with power of 80% if the within recruitment chain and within intervention-delivery group correlation coefficient is no greater than 0.1. As an illustration of how this can be used for planning the large randomized trial, suppose in this pilot study, proportion of participants take PrEP risk screening is 85% and 50% for Gender-Enhanced workshop and Information-Only Workshop respectively while the minimally clinically relevant improvement, on extrinsic grounds, is an improvement of 15 percentage points. Then, N=240 per group would be required in the RCT. The above plan will allow us to assess feasibility and acceptability, estimate factors influencing intervention parameters, and examine the range of possible effect sizes for our primary outcome. Therefore, the information collected from this pilot study should put us in an excellent position to conduct a future full-scale RCT.

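### The mediator model estimates the pre-to-post effect as a difference in mean change and does not adjust for the collected pre-test score: valid, but modestly less precise than it could be

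*SAP*

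**What the plan says.** The mediator paragraphs of the SAP's Data Analysis section use a linear model with GEE "to compare the mean difference between the two intervention groups from post-test to pre-test, and from 3-month follow-up to post-test". The model has a term for condition (b1), two visit indicators (b2, b3) and two condition-by-visit terms (b4, b5). The SAP interprets the contrasts itself: "The regression coefficient b4 represents the group difference in change of the outcome Y (i.e., the potential mediators) from pre- to" post-intervention, and "it is b5-b4 (NOT b5) that represents the group difference in change of Y from post-intervention to 3-month FU".

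Other covariates enter conditionally: the mediator model is described as a "difference of difference analysis), adjusting for age and other confounders if necessary". For the main outcomes the same section admits further characteristics "if these factors differ substantially by condition at baseline and are also associated with the outcome". The pre-test mediator score is not among the examples.

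The score is available. The pilot-study part of Assessment Instruments in the Protocol lists "Hypothesized mediators and effect modifiers to be ascertained at each assessment", and participants complete a questionnaire before either intervention.

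The precision statements in the SAP's power considerations concern other quantities. The sample-size sentence, "with total sample size of 100 participants we are still able to declare a difference of 33 to 36 percentage points", is about the binary primary outcome. Key parameters are to be reported "together with two-sided 95% confidence intervals". No interval width, power or pre/post correlation is given for any mediator.

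**The concern.** In this model the pre-test score is only one of three outcome records per woman, and b1 leaves the pre-test difference between conditions free. The pre-to-post effect is therefore each condition's mean change, subtracted. A change score gives the pre-test value a weight of exactly 1. When the pre/post correlation is below 1 and the conditions have equal expected pre-test means, that weight is too large and the interval is wider than it need be.

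Two things depend on it. The power considerations give weight to interval estimates and look to the continuous measures for signal in a small sample. The last mediator step also carries into the outcome models only those mediators that the intervention has altered, so imprecision in b4 affects which mediators are examined at all.

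**Working it through.** There is no mediator figure in the documents to reproduce, so the check compares the planned estimator with a baseline-adjusted one.

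**Inputs.** From the documents: 100 women in total, about 50 per condition; two-sided 95% intervals; 16 randomised seeds, so 100/16 ≈ 6 women per chain; correlation within chain of at most 0.1 (stated for the binary outcome). Assumed: mediator SD = 1 at every visit; pre/post correlation r of 0.3, 0.5 or 0.7.

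**Step 1: what b4 is.** The model is saturated in condition and visit, so with complete data it reproduces the six condition-by-visit means. Fitting it to simulated complete data (16 chains of 6) gave b4 = -0.160 and b5-b4 = 0.231, identical to the raw differences in mean change under both independence and exchangeable working correlation. GEE does not recover the adjustment.

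**Step 2: pre-to-post, no clustering.** With n = 50 per condition:
- change score: variance = (2/n) × 2(1 - r)
- adjusted: variance = (2/n) × (1 - r²)
- ratio, adjusted to change score = (1 + r)/2

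**Step 3: pre-to-post, chain effects stable over time.** With intracluster correlation 0.1 and chains of 6, a stable chain effect cancels from the change score, so its variance is as in Step 2. In the adjusted estimate a share (1 - r) of the chain effect remains:
- adjusted: variance = (2/n) × [(1 - r²) + (6 - 1) × 0.1 × (1 - r)²]
- ratio, adjusted to change score = (1 + r)/2 + 0.25(1 - r) = 0.75 + 0.25r

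Half-widths of the 95% interval are 1.96 × √variance, in SD units:

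| r | Change score | Adjusted, no clustering | Change score wider by | Adjusted, stable chains | Change score wider by |
|---|---|---|---|---|---|
| 0.3 | 0.464 | 0.374 | 24% | 0.421 | 10% |
| 0.5 | 0.392 | 0.339 | 15% | 0.367 | 7% |
| 0.7 | 0.304 | 0.280 | 8% | 0.292 | 4% |

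Chain effects that are only partly stable move the result back towards the unclustered columns.

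**Step 4: post-test to 3 months (b5-b4).** Adjusting Y2 - Y1 for the pre-test score reduces its variance by (r02 - r01)², where r01 and r02 are the correlations of the pre-test with the post-test and 3-month scores. If these are equal the gain is zero. With r01 = 0.6, r02 = 0.36 and a post-test to 3-month correlation of 0.6, the variance goes from 0.80 to 0.80 - 0.24² = 0.7424, a width ratio of √(0.80/0.7424) = 1.04. In simulations with equal correlations the SD ratio was 0.99 to 1.00.

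**Step 5: when the two estimates disagree.** Let d be the observed pre-test difference between conditions. The adjusted estimate minus the change-score estimate is (1 - r)d.
- If d is chance, the change score is off by -(1 - r)d. The standard error of d is √(2/50) = 0.20 SD, or 0.20 × √1.5 ≈ 0.24 SD with the Step 3 design effect of 1 + 5 × 0.1. At r = 0.5 and d = 0.2 the shift is 0.10 SD.
- If d is systematic and persists, the adjusted estimate is off by (1 - r)d. For assumed d of 0.1 to 0.3 SD this runs from 0.3 × 0.1 = 0.03 (r = 0.7) to 0.7 × 0.3 = 0.21 SD (r = 0.3).

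**The case against.** The strongest reply is that the planned model is correct for the question asked. The revised aims speak of changes in the mediators, the model targets changes, and its coefficients are interpreted correctly. That stands: a reader might infer that the mediator analysis is biased or wrong, and nothing in the documents supports that.

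The second reply concerns recruitment. The Protocol randomises only the seeds. Later women join the condition of the Peer Health Advocate who invited them, and she has already taken part and carries materials with PrEP information. Recruits' pre-test scores may therefore differ by condition for reasons other than chance. By Step 5, a persisting difference of 0.3 SD at r = 0.5 would move the adjusted estimate by 0.15 SD, more than the half-width saved (0.392 - 0.339 = 0.053 SD). This also stands. It rules out the tempting claim that adjustment is free, and it is why both estimates are needed.

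The third reply is about size. The variance ratios in Step 2 could be read as worth 54%, 33% or 18% more women (2/(1 + r) - 1). Those figures assume independent women and correlations that the documents do not give; Step 3 shows how much stable chain effects shrink the gain. Nor can the point be extended to every mediator interval, because b5-b4 hardly changes.

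Finally, the planned estimate is not wholly unadjusted, since age and other confounders may enter, and these are non-primary outcomes in a pilot. Both are true and limit the weight of the point. Neither brings the pre-test score in as a covariate.

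**Conclusion.** The point holds as a modest loss of efficiency confined to b4. With 50 women per condition, equal SDs, complete data and r between 0.3 and 0.7, the planned interval is wider than a pre-test-adjusted one by about 8% to 24% without clustering, and by about 4% to 10% under the stable-chain assumption. The correlation, the chain size and the stability of chain effects are all assumptions. The post-test to 3-month contrast is essentially unaffected.

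The precision advantage presumes equal expected pre-test means in the two conditions. Seed-level randomisation supports that, but recruitment through exposed peers puts it in some doubt, so the documents do not justify dropping the change-score analysis.

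**What to change.** In the mediator paragraphs of the SAP, specify a model for the post-test and 3-month scores only, with the same chain-level GEE and the same conditional adjustment for age and confounders:

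E(Y) = c0 + c1·X + c2·V + c3·X·V + c4·(pre-test score), with V = 1 at 3 months.

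Report c1 (condition effect at post-test) and c1 + c3 (condition effect at 3 months), each with its interval. The term c3 keeps the post-test to 3-month contrast that the SAP now obtains as b5-b4.

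Alongside it:
- Show pre-test means and SDs of each mediator by condition, separately for seeds and recruits.
- Report the existing difference-in-difference model in the same table.
- State in advance that disagreement between the two models will be read as a sign of pre-test differences between conditions, and not only as a matter of precision.

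The cost is SAP wording and some extra table columns; no new data are needed. The effect-modifier section, updated in December 2022, already gives observed subgroup counts. The change should therefore be dated, with a statement of whether mediator results by condition had been seen when it was made.
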